7.6 Dose Adjustments and Adverse Reaction Management

Dose adjustments for toxicity of duvelisib and nivolumab are detailed below and are excerpted from the duvelisib package insert and the nivolumab package insert^{11,22}. Where appropriate, management guidelines for immune-related adverse events in patients receiving immune checkpoint therapy, from the American Society of Clinical Oncology (ASCO) Practice Guidelines has been included²³. The table below is not comprehensive and clinicians should refer to the ASCO Practice Guidelines for more detailed management recommendations. When possible, biopsies should be pursued to help determine the study drug(s) responsible for a given toxicity.

Table 7.6 Dose Adjustments for Toxicity

Toxicity	Adverse Reaction Grade	Recommended Management
Nonhematologic Adverse Reactions		
Infections	Grade 3 or higher infection	
Duvelisib
 
 - Withhold duvelisib until resolved - Resume at the same or reduced dose 
Nivolumab
 
 - Withhold nivolumab until resolved - Resume at same dose
	Clinical CMV infection or viremia (positive PCR or antigen test)	
Duvelisib
 
 - Withhold duvelisib until resolved - Resume at the same or reduced dose - If duvelisib is resumed, monitor patients for CMV reactivation by PCR or antigen test at least monthly

Toxicity	Adverse Reaction Grade	Recommended Management
		
Nivolumab
 
 - Withhold nivolumab until resolved - Resume at same dose
	PJP	
Duvelisib
 
 - For suspected PJP, withhold duvelisib until evaluated - For confirmed PJP, discontinue duvelisib 
Nivolumab
 
 - Withhold nivolumab until resolved
Non-infectious diarrhea or colitis	Mild/moderate diarrhea (Grade 1-2, up to 4 stools per day over baseline) and responsive to antidiarrheal agents, OR Asymptomatic (Grade 1) colitis	
Duvelisib
 
 - No change in dose - Initiate supportive therapy with antidiarrheal agents as appropriate - Monitor at least weekly until resolved 
Nivolumab
 
 - Continue nivolumab or hold until symptoms resolve

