	Mild/moderate diarrhea (Grade 1-2, up to 6 stools per day over baseline) and unresponsive to antidiarrheal agents	
Duvelisib
 
 - Withhold duvelisib until resolved - Initiate supportive therapy with systemic steroids - Monitor at least weekly until resolved - Resume at a reduced dose - Gastroenterology consultation, recommend endoscopy and biopsy 
Nivolumab
 
 - Withhold nivolumab until resolved - Resume at same dose - Support with systemic steroids, gastroenterology consultation, recommend endoscopy and biopsy
	Abdominal pain, stool with mucus or blood, change in bowel habits, peritoneal signs, OR Severe diarrhea (Grade 3, >6 stools per day over baseline)	
Duvelisib
 
 - Withhold duvelisib until resolved - Initiate supportive therapy with enteric acting steroids (e.g., budesonide) or systemic steroids - Monitor at least weekly until resolved - Resume at a reduced dose

Toxicity	Adverse Reaction Grade	Recommended Management
		
 - For recurrent Grade 3 diarrhea or recurrent colitis of any grade, discontinue duvelisib 
Nivolumab
 
 - Withhold nivolumab until resolved - Resume at same dose - Systemic steroids, gastroenterology consultation and biopsy - If no improvement in 3-5 days, consider addition of infliximab
	Life-threatening, grade 4	
Duvelisib
 
 - Discontinue duvelisib 
Nivolumab
 
 - Permanently discontinue nivolumab - Systemic steroids, gastroenterology consultation and biopsy - If no improvement in 3-5 days, consider addition of infliximab
Cutaneous reactions	Grade 1	
Duvelisib
 
 - No change in dose - Initiate supportive care with emollients, antihistamines (for pruritus), or topical steroids - Monitor closely 
Nivolumab
 
 - Continue nivolumab - Support with topical emollients and/or mild-moderate potency topical corticosteroids
	Grade 2	
Duvelisib
 
 - Consider holding duvelisib, restart at same dose - Initiate supportive care with emollients, antihistamines (for pruritus), or topical steroids - Monitor closely 
Nivolumab
 
 - Consider holding nivolumab until resolved - Resume at same dose once improved to grade 1

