Toxicity	Adverse Reaction Grade	Recommended Management
		
 - Support with topical emollients and/or mild-moderate potency topical corticosteroids - Consider systemic steroids at 1mg/kg and taper over 4 weeks - Consider skin biopsy
	Grade 3	
Duvelisib
 
 - Withhold duvelisib until resolved - Initiate supportive care with emollients, antihistamines (for pruritus), or topical steroids - Monitor at least weekly until resolved - Resume at reduced dose - If severe cutaneous reaction does not improve, worsens, or recurs, discontinue duvelisib 
Nivolumab
 
 - Hold nivolumab until resolved - Resume at same dose once improved to grade 1 - Support with topical emollients and high-potency steroids, dermatology consultation - Systemic steroids at 1-2mg/kg and taper over 4 weeks - Consider dermatology consultation - Skin biopsy recommended
	Grade 4	
Duvelisib
 
 - Discontinue duvelisib 
Nivolumab
 
 - Hold nivolumab - Dermatology consultation to determine if appropriate to resume upon resolution - Systemic steroids administered IV -Skin biopsy recommended
	SJS, TEN, DRESS (any grade) or life-threatening skin toxicity	
Duvelisib
 
 - Discontinue duvelisib 
Nivolumab
 
 - Discontinue nivolumab

Toxicity	Adverse Reaction Grade	Recommended Management
Pneumonitis without suspected infectious cause	Grade 1 – asymptomatic. If repeat imaging with progression	
Duvelisib
 
 - Withhold duvelisib - If pneumonitis recovers to Grade 0 or 1, duvelisib may be resumed at same dose - If no improvement should treat as grade 2 
Nivolumab
 
 - Withhold nivolumab until resolved - Resume at same dose - If no improvement, treat as grade 2

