8.1 Dose Limiting Toxicities

Acute dose limiting toxicities (DLTs) are defined as any of the following AEs and laboratory abnormalities considered possibly, probably, or definitely related to study treatment that occur any time from the initial dose of duvelisib in combination with nivolumab through day 28 of treatment. Toxicities occurring from day 29 through 28 days after completion of treatment will be considered late toxicities. Only acute DLTs will be considered for decisions to continue enrollment at the current dose level or proceed to the next dose level. Acute and late toxicities will be considered when deciding on the RP2D and will be discussed in monthly Data Safety Monitoring Board (DSMB) meetings. See Section 15.0 for further details.

Severity of adverse events will be graded by National Cancer Institute Common Terminology Criteria for Adverse Events version 5.0 (CTCAE v5.0). A goal of $\leq 33\%$ DLTs at each dose level will be considered acceptable.

Whenever possible, biopsies are recommended if they can be done safely to help determine between immune-related and other etiologies of toxicity, particularly for rash and colitis. Biopsies for elevated liver enzymes and/or for pneumonitis should be considered if deemed feasible and safe in the context of risk:benefit evaluation. General criteria for consideration of biopsy:

- Diarrhea/colitis
 - Biopsy proven grade ≥ 3 immune-related colitis
 - Diarrhea of grade ≥ 3 that does not respond to treatment with steroids within 5 days
- Pneumonitis
 - Immune-related pneumonitis grade ≥ 2

- Any grade ≥ 3 pneumonitis
- Hematologic abnormalities
 - Neutropenia grade 4 despite holding duvelisib for 7 days
 - Thrombocytopenia grade ≥ 3 with bleeding
 - Thrombocytopenia grade 4
- Other immune-related toxicities
 - Any grade ≥ 3 toxicity that does not respond to treatment within 5d
- For the remainder of non-hematologic toxicities, grade ≥ 3

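### Section 8.1 heads its DLT list as biopsy criteria and exempts a narrow set of grade 4 events that respond within 5 days, so the 1-of-6 rule can escalate past them

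*Combined protocol and SAP*

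**What the plan says.** Section 8.1 defines acute DLTs as the events listed after the definition, if at least possibly related to treatment and occurring by day 28. The only list that follows is introduced as "General criteria for consideration of biopsy". Its lines are:

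- **Unconditional:** biopsy-proven immune-related colitis of grade 3 or higher; immune-related pneumonitis of grade 2 or higher and any pneumonitis of grade 3 or higher; grade 4 thrombocytopenia.
- **Conditional on response:** diarrhea of grade 3 or higher "that does not respond to treatment with steroids within 5 days"; for other immune-related toxicities, any grade 3 or higher "toxicity that does not respond to treatment within 5d".
- **Other hematologic lines:** grade 4 neutropenia despite 7 days off duvelisib; thrombocytopenia of grade 3 or higher with bleeding.
- **Catch-all:** grade 3 or higher, for the remaining non-hematologic toxicities.

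On use, 8.1 says: "Only acute DLTs will be considered for decisions to continue enrollment at the current dose level or proceed to the next dose level". Section 14.1.1 takes its DLT definition from 8.1, sets the MTD as the highest level with at most 1 DLT in 6, and makes the MTD a ceiling for the RP2D.

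Table 7.6 (Section 7.6) discontinues duvelisib in these rows, with no condition on response:

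- diarrhea/colitis, "Life-threatening, grade 4": both drugs end;
- ALT/AST above 20 x ULN: both drugs end;
- "SJS, TEN, DRESS (any grade) or life-threatening skin toxicity": both drugs end;
- cutaneous grade 4: duvelisib ends and nivolumab is held ("Dermatology consultation to determine if appropriate to resume upon resolution").

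**The concern.** The heading leaves 8.1 without a labelled DLT list. If the list is read as the DLT list, its two conditional lines release a grade 4 event as readily as a grade 3 one, provided it responds within 5 days. The catch-all does not recover these events, because it covers only toxicities not already dealt with. The result is uneven: a related non-immune grade 3 event counts whether or not it responds, while a grade 4 immune-related hepatitis that responds does not.

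At stake is the phase I count. It decides whether the next dose opens and sets the ceiling for the dose given to the 24 additional phase II patients (Section 14.0).

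**Working it through.** **1. Is it the DLT list?** Its contents say yes. Biopsy-proven colitis cannot be a reason to consider a biopsy, and grade 4 neutropenia is not a natural biopsy trigger. Sections 3.2.2 and 14.1.1 also point to 8.1 for the definition. Section 15.0, to which 8.1 refers for further detail, contains no DLT criteria.

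**2. Which events fall through?** Setting 8.1 beside Table 7.6, for related grade 4 events in days 1-28:

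| Event | Table 7.6, duvelisib | DLT under 8.1 if it responds within 5 days? |
|---|---|---|
| Diarrhea, immune-related colitis proven by biopsy | discontinue | yes |
| Diarrhea, no such proof | discontinue | **no** |
| Pneumonitis | discontinue | yes |
| ALT/AST or skin, classed as immune-related | discontinue | **no** |
| ALT/AST or skin, not classed as immune-related | discontinue | yes (catch-all) |

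Grade 4 neutropenia is not an example, because Table 7.6 withholds duvelisib rather than ending it.

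**3. Effect on the rule (14.1.1).** A level passes with at most 1 DLT in the first 3 patients and at most 1 in 6.

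- One exempt event and one listed DLT in 6: as written 1 of 6, passes; counted 2 of 6, stops.
- Two exempt events in 6: as written 0 of 6, passes; counted 2 of 6, stops.

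**4. Size.** The documents give no operating characteristics for the phase I rule, so there is no plan figure to reproduce for it. The only DLT-based figures are the early-stop probabilities in 14.2.3.3 (0.0885, 0.3332, 0.6727, 0.9128). They reproduce exactly with a look after each patient from the third, but they say nothing about the exemption.

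Let p be the share of patients with a listed DLT and q the share with an exempt event and no listed DLT. Both are assumptions.

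P(pass) = (1 - p)^6 + 6p(1 - p)^5

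- As written, p = 0.15: 0.3771 + 0.3993 = 0.7765
- Counted, q = 0.005 (p + q = 0.155): 0.3640 + 0.4007 = 0.7647
- Counted, q = 0.01 (p + q = 0.16): 0.3513 + 0.4015 = 0.7528

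The share of level decisions that change is the difference: 0.7765 - 0.7647 = 0.0118 and 0.7765 - 0.7528 = 0.0237. At q = 0.02 it is 0.7765 - 0.7287 = 0.0478, and at q = 0.05 it is 0.7765 - 0.6554 = 0.1211. Nothing in the documents supports rates that high.

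At q = 0.01 the change splits into one listed DLT with at least one exempt event, 6 x 0.15 x (0.85^5 - 0.84^5) = 0.0229, and at least two exempt events with no listed DLT, 0.85^6 - 0.84^6 - 6 x 0.01 x 0.84^5 = 0.0008. The mixed case dominates.

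**5. Is q likely to be large?** Sections 11.2 and 11.3 give median onsets for duvelisib of 4 months (diarrhea/colitis) and 3 months (cutaneous), against a 28-day window. Section 11.3 also gives a median cutaneous event duration of 1 month, so response of a severe skin event within 5 days looks unusual. These are not data on the combination.

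**The case against.** The strongest reply is that the 5-day condition is deliberate and the gap very small. The authors wrote unconditional lines where they wanted them, and put grade 3 or higher, not grade 3, in the conditional ones. The grade 4 diarrhea row of Table 7.6 itself calls for a biopsy, and proven immune-related colitis of grade 3 or higher always counts. Non-immune skin and liver events count under the catch-all. Section 8.1 also requires acute and late toxicities to be weighed for the RP2D and discussed at monthly DSMB meetings, and Section 10.1 gives power to suspend accrual. The top dose, 25 mg BID, is below the 75 mg BID monotherapy MTD in lymphoma (Section 7.5).

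Much of this stands. The exempt set is narrow and the review is mandatory, with only its outcome left to judgment. Intent cannot be settled: 14.2.3.3 describes DLTs in general as grade 3 and 4, but refers back to 8.1. What does not follow is that the gap is closed. None of these safeguards changes the count on which escalation depends.

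A reader might go further and infer that Table 7.6 contradicts 8.1, so that every event ending duvelisib must be a DLT. The documents do not support that. The table gives recommended management drawn mainly from package inserts, says of itself "The table below is not comprehensive", and nowhere claims to define DLTs. Such a trigger would also bring in events below grade 4, such as confirmed PJP or recurrent colitis of any grade.

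**Conclusion.** The point holds in limited form. Section 8.1 has a misheaded DLT list, and its two 5-day conditions leave a narrow group of related grade 4 events in days 1-28 outside the escalation count. The consequence of one such event beside one listed DLT is certain: the level passes as written and would stop if the event counted. How often this happens is unknown and probably low, with 1.2% to 2.4% of level decisions changing under the assumed rates of 15% for listed DLTs and 0.5% to 1% for exempt events.

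It would be wrong to infer that grade 4 toxicity in general escapes the rule, or that these events would go unreviewed. Nor is the same effect established for the phase II toxicity boundary: 14.2.3.3 speaks of DLTs but tabulates SAEs, and life-threatening events are SAEs under 8.2.1. This is worth correcting because it bears on a binding safety rule and costs little, not because a large effect has been shown.

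**What to change.** In Section 8.1:

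1. Put the DLT list under its own heading, separate from the biopsy advice.
2. Limit both 5-day response conditions (diarrhea, other immune-related toxicity) to grade 3.
3. Add: *Any related day 1-28 grade 4 non-hematologic event is a DLT regardless of response.*

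The added sentence reaches only what the two conditional lines now release, since other non-hematologic grade 4 events already count. It includes any grade 4 immune-related event that Table 7.6 does not list. The hematologic lines stay as they are.

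No new data are needed. The cost is that escalation stops slightly more often: under the same assumptions, the chance of passing a level falls from 77.6% to 76.5% (exempt rate 0.5%) or 75.3% (1%). Every additional stop is at a level where a related grade 4 event occurred.

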	Moderate (Grade 2) symptomatic pneumonitis	
Duvelisib
 
 - Withhold duvelisib - Treat with systemic steroid therapy - If pneumonitis recovers to Grade 0 or 1, duvelisib may be resumed at reduced dose - If non-infectious pneumonitis recurs or patient does not respond to steroid therapy, discontinue duvelisib 
Nivolumab
 
 - Withhold nivolumab until resolved to grade 0-1 - Resume at same dose - Prednisone 1-2mg/kg/d, with long taper - Consider pulmonology consultation, bronchoscopy and biopsy, empiric antibiotics - Monitor closely, if no improvement in 2-3 days treat as grade 3
	Severe (Grade 3) or Grade 4 life-threatening pneumonitis	
Duvelisib
 
 - Discontinue duvelisib - Treat with systemic steroid therapy 
Nivolumab
 
 - Permanently discontinue nivolumab - Treat with high dose IV steroids, consider infliximab, empiric antibiotics - Pulmonary and infectious disease consultations and biopsy if able
ALT/AST elevation	3 to 5 x upper limit of normal (ULN) (Grade 2)	
Duvelisib
 
 - Maintain duvelisib dose - Monitor at least weekly until return to < 3 x ULN

Toxicity	Adverse Reaction Grade	Recommended Management
		
Nivolumab
 
 - Withhold nivolumab until resolved to grade 1 - Resume at same dose - Consider steroids if abnormality persists and clinical symptoms
	> 5 to 20 × ULN (Grade 3)	
Duvelisib
 
 - Withhold duvelisib and monitor at least weekly until return < 3 × ULN - Resume duvelisib at same dose (first occurrence) or at a reduced dose for subsequent occurrence 
Nivolumab
 
 - Permanently discontinue nivolumab - Start steroids with methylprednisolone at 1-2mg/kg/d - Consider liver biopsy
	> 20 × ULN (Grade 4)	
Duvelisib
 
 - Discontinue duvelisib - Systemic steroid treatment 
Nivolumab
 
 - Permanently discontinue nivolumab - Start steroids with methylprednisolone at 1-2mg/kg/d - Avoid infliximab - Hepatology consultation, consider liver biopsy
Hematologic Adverse Reactions		

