Neutropenia	Absolute neutrophil count (ANC) 500 to 1000 cells/µL	
Duvelisib
 
 - Maintain duvelisib dose - Monitor ANC at least weekly 
Nivolumab
 
 - Withhold nivolumab until resolved if it is felt to contribute to the neutropenia, and otherwise continue nivolumab as previously - Resume at same dose
	ANC less than 500 cells/µL	
Duvelisib
 
 - Withhold duvelisib

Toxicity	Adverse Reaction Grade	Recommended Management
		
 - Monitor ANC until > 500 cell/uL - Resume duvelisib at same dose (first occurrence) or at a reduced dose for subsequent occurrence 
Nivolumab
 
 - Withhold nivolumab until resolved if it is felt to contribute to the neutropenia, and otherwise continue nivolumab as previously - Resume at same dose 
*If concern for auto-immune neutropenia, then hold nivolumab and follow practice guidelines

Thrombocytopenia	Platelet count 25K to < 50K cells/ μ L (Grade 3) with Grade 1 bleeding	
Duvelisib
 
 - No change in dose - Monitor platelet counts at least weekly 
Nivolumab
 
 - Withhold nivolumab until resolved - Resume at same dose
	Platelet count 25K to < 50K cells/ μ L with grade 2 bleeding OR platelet count <25K cells/ μ L (Grade 4)	
Duvelisib
 
 - Withhold duvelisib - Monitor platelet count until > 25K cells/uL and resolution of bleeding if applicable. - Resume duvelisib at same dose (first occurrence) or resume at a reduced dose for subsequent occurrence 
Nivolumab
 
 - Withhold nivolumab until resolved - Resume at same dose 
*If concerned for autoimmune thrombocytopenia, hold nivolumab and follow practice guidelines

Table 7.7 Dose Reductions for Duvelisib

Initial Dose	Decreased Dose
15mg Daily	None

25mg Daily	15mg Daily
25mg BID	25mg Daily

Note: If patient is on dose level 1, 15mg daily and has a dose interruption, duvelisib will be resumed at same dose. If patient subsequently requires another dose interruption at this level for the same toxicity, duvelisib should be discontinued. No more than 2 dose reductions for the same side effect are allowed for any patient, irrespective of starting dose.

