7.10.2 Permitted therapy

- Inactivated influenza vaccination is permitted.
- Topical, ocular, intra-articular, intranasal and inhalational corticosteroids are permitted.
- Oral corticosteroids for premedication prior to scans are permitted.
- Systemic corticosteroids are permitted for treatment of AEs.
- Use of growth factors are permitted.
- Palliative care evaluation for symptom control can be offered to any patient on trial.
- For patients requiring surgery other than treatment-related biopsies, duvelisib should be held for 2 weeks before and after if possible. Duvelisib may be restarted sooner than 2 weeks, in consultation with the attending surgeon if the subject recovers and surgery-related AEs have decreased to grade 1 or baseline.

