11.5 Neutropenia

Patients with hematologic conditions treated with duvelisib frequently developed neutropenia. CBC with differential should be checked at least every 2 weeks during cycle 1, and more frequently for those with ANC < 1000 cells/ μ L. Withhold duvelisib if ANC < 500 cells/ μ L, monitor weekly and resume at same dose of the first occurrence or at a decreased dose for subsequent occurrence. Duvelisib can be resumed when ANC > 100 is reached in the absence of signs of infection. G-CSF may be used per ASCO guidelines.

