14.1. Phase I Portion of the Study

14.1.1. Study Design

The primary objectives of the phase I portion are to determine the maximum tolerated dose (MTD) of duvelisib when combined with anti-PD1 therapy nivolumab, and to decide on its recommended phase II dose (RP2D). Dose escalation will follow the decision rule in the following table, using the three dose levels defined in Section 7.5 (i.e., 15mg Daily, 25mg Daily, and 25mg BID), starting from the lowest dose. The MTD is defined to be the highest dose level at which no more than 1 of 6 treated patients experiences a DLT (DLT is defined in Section 8.1). Cohorts of three to six patients each will be treated at a dose level. Patients should have taken 75% of pills to be included in analysis of their respective cohort, as assessed through pill counts and pill diary. Only toxicities observed during the first treatment cycle will affect dose escalation. Late toxicities observed will be discussed at monthly data safety monitoring boards to determine if dose adjustments should be made.

After MTD is determined, we will decide on RP2D based on an overall consideration of DLT data, as well as immune cell profiling with laboratory correlates. For this purpose, our decision rule in the following table is a slight modification of the standard “3+3” to make sure 6 patients will be accrued at each safe dose in order to have enough patients for laboratory evaluations. RP2D should not be higher than MTD. If the MTD is not reached, RP2D will be decided based on safety data from acute and late toxicities as well as immune cell profiling data by the investigators (see section 13.1).

DECISION RULES FOR DOSE LEVEL ESCALATION

No. of patients with DLT's at this dose level	No. of patients treated at this dose level	Action
≤1	3	Treat 3 more patients at this dose level.
≤1	6	Treat 3 patients at the next higher dose level (or if at the highest level, stop the trial, and declare the dose at this level to be the MTD).

>1	3 or 6	Stop dose escalation. The previous dose is defined as MTD.
----	--------	--

Cohorts need not be completed if clear decisions can be made on the basis of an incomplete cohort. For example, if the first two patients in an intended cohort of three experience DLT's, escalation can be stopped without accruing the third member of the cohort.

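### Section 8.1 has no DLT line for neutropenia with fever, so read literally a short first-cycle episode is left out of the 1-of-6 rule; the effect is probably small and one line would close it

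*Combined protocol and SAP*

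**What the plan says.** Section 8.1 defines acute DLTs as listed events at least possibly related to treatment, from the first combined dose through day 28. The hematologic list has three entries. One concerns neutropenia, "Neutropenia grade 4 despite holding duvelisib for 7 days", and the other two concern thrombocytopenia. The residual entry reads "For the remainder of non-hematologic toxicities, grade" 3 or higher. A separate entry for other immune-related toxicities counts grade 3 or higher events that have not responded to treatment within 5 days.

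The count drives escalation. Section 8.1 states "Only acute DLTs will be considered for decisions to continue enrollment at the current dose level or proceed to the next dose level", and section 14.1.1 states "The MTD is defined to be the highest dose level at which no more than 1 of 6 treated patients experiences a DLT".

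Table 7.6 places neutropenia under "Hematologic Adverse Reactions" and infections under the non-hematologic heading. Below an ANC of 500 it withholds duvelisib, instructs "Monitor ANC until > 500 cell/uL" and then allows resumption. Section 7.10.2 says "Use of growth factors are permitted" and section 11.5 says "G-CSF may be used per ASCO guidelines". No section says how neutropenia with fever is scored.

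**The concern.** Requiring grade 4 neutropenia to persist through a 7-day hold is a legitimate choice when the patient has no fever. Section 8.1 makes no exception when fever is present. With the hold, monitoring and G-CSF that the protocol allows, an episode can end before day 7 and meet no listed criterion.

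The protocol recognises the distinction elsewhere: section 11.5 makes resumption of duvelisib depend on there being no signs of infection. DLT scoring does not follow suit.

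At stake is the written escalation rule. With a limit of 1 in 6, one unscored patient can change the action at a level, and leaving the event out can only favour escalation. The silence also means that two people could score the same patient differently, depending on whether they treat the fever as part of the hematologic event.

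**Working it through.** **1. Does any criterion in 8.1 reach the event?** Take treatment-related neutropenia with fever in cycle 1 that recovers before 7 days of hold.

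| Route | Does it count? |
|---|---|
| Neutropenia line | No, unless it recurs in the window and stays grade 4 through a new 7-day hold |
| Thrombocytopenia lines | No |
| Other immune-related, grade 3 or higher, unresponsive at 5 days | Arguably, if immune-related and slow to respond. Table 7.6 does contemplate autoimmune neutropenia, but the word *other* follows the hematologic list |
| Residual grade 3 or higher line | Only through a separate non-hematologic event, such as a grade 3 or higher infection |
| General grade 3 and 4 wording in 14.2.3.3 | No. It refers back to 8.1 for the detail and concerns phase II monitoring |

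The bullets in 8.1 follow a sentence about when to consider biopsy. The section nevertheless opens by defining DLTs as the events that follow, and a 7-day-hold criterion makes sense only as a DLT rule, so I read them that way.

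**2. The plan's own figures.** The plan gives no operating characteristics for the 1-of-6 rule. The phase II toxicity rule in 14.2.3.3 uses the same DLT definition. With a Beta(0.5, 0.5) prior and a hold when the posterior probability of a rate above 30% exceeds 0.7, every row of its boundary table reproduces. So do its early-stopping probabilities: 0.0885, 0.3332, 0.6727 and 0.9128 at true rates of 0.1, 0.2, 0.3 and 0.4. (The inequality printed in the text runs the other way; the table fits this direction.)

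**3. The 1-of-6 rule.** A level that ends with at most 1 DLT in 6 also had at most 1 in its first 3, so

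P(pass) = P(Binomial(6, p) ≤ 1) = (1 − p)^5 × (1 + 5p).

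Let o be the rate of other DLTs and f the rate of uncounted episodes in patients with no other DLT. Both are assumed, because the documents give neither. As written, p = o; with the episodes counted, p = o + f.

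| o | f | P(pass) | Change |
|---|---|---|---|
| 10% | as written | 0.9^5 × 1.50 = 0.8857 | |
| 10% | 1% | 0.89^5 × 1.55 = 0.8655 | −2.0 points |
| 10% | 2% | 0.88^5 × 1.60 = 0.8444 | −4.1 points |
| 20% | as written | 0.8^5 × 2.00 = 0.6554 | |
| 20% | 1% | 0.79^5 × 2.05 = 0.6308 | −2.5 points |
| 20% | 2% | 0.78^5 × 2.10 = 0.6063 | −4.9 points |

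Each change is the probability that the action at that level would differ.

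**4. Sensitivity.** If the episodes are instead independent of other DLTs, p = 1 − (1 − o)(1 − f). At o = 10% and f = 2%, p = 0.118 and P(pass) = 0.849, a fall of 3.7 points. At a higher assumed f of 5%, the fall is 10.9 points with no overlap (0.7765) and 9.8 points under independence (p = 0.145, P(pass) = 0.788). Nothing in the documents supports a rate that high.

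**5. Chance of meeting the problem.** If all 18 phase I places fill, the chance of at least one such episode is 1 − (1 − f)^18, which is 17% at f = 1% and 30% at f = 2%.

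**The case against.** The strongest reply is that the gap is narrow and the event unlikely. Most of this stands.

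- **Infection is already covered.** A reader might infer from the black box warning in section 11.1 that serious infections escape the DLT count. They do not: Table 7.6 files infections as non-hematologic, so a related grade 3 or higher infection in the window counts with or without neutropenia. What is left is neutropenia with fever and no such event.
- **Timing.** Section 11.1 puts the median time to infection at 3 months, well outside the 28-day window. This suggests few first-cycle events.
- **Population.** Section 11.5 reports frequent neutropenia in hematologic patients. Here entry requires an ANC of at least 1500 (section 4.1), and section 15.0 expects fewer toxicities than in hematologic disease.
- **Other safeguards.** Acute and late toxicities inform the RP2D, the DSMB meets monthly, and the DSMB and DSMC can suspend accrual. The top dose of 25 mg BID is one third of the 75 mg BID monotherapy MTD (section 7.5). The rule is also stricter than the 33% goal in 8.1: at a true DLT rate of 33.3% a level passes 35.2% of the time.
- **Certain exclusion is too strong.** Section 8.1 grades by CTCAE v5.0, whose treatment of neutropenia with fever is not reproduced in the documents. They show a list that omits the event when read literally, and room for differing scores. They do not show that every such episode would go unscored.

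None of these points puts the event on the list that decides escalation.

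**Conclusion.** The point holds as a cheap improvement. Read literally, 8.1 does not count first-cycle treatment-related neutropenia with fever that recovers before the 7-day criterion is met, apart from the exceptions in step 1. No other section closes the gap.

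The effect is probably small. At assumed rates of 1% to 2%, a level's pass probability is 2.0 to 4.1 points higher than if the episodes counted, with 10% other DLTs, and 2.5 to 4.9 points higher with 20%. These figures rest on assumed rates, on no overlap with other DLTs, and on patients behaving independently. A reader might infer that escalation is unsafe or that the MTD will be materially too high. The documents do not support that: they give no event rate, what they say on timing and population points to the low end, and the event remains visible to the DSMB and in the RP2D choice.

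**What to change.** Add one line to the hematologic list in 8.1: *febrile neutropenia of grade 3 or higher by CTCAE v5.0, where the episode as a whole is judged at least possibly related to study treatment, from first dose through day 28, regardless of duration or G-CSF use.*

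CTCAE v5.0 is already the grading standard in 8.1, so no new cut-offs are needed. Tying relatedness to the whole episode keeps out a fever with another clear cause in a patient whose neutropenia is drug-related. Keep the 7-day rule unchanged for neutropenia without fever.

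No new procedure is required: section 11.5 already asks for a CBC with differential at least every 2 weeks in cycle 1, and adverse events are recorded from the start of treatment. The cost is slightly more conservative escalation, by the amounts in step 3.
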